It is theoretically claimed that mindfulness meditation can positively impact perceived stress, known also as stress appraisal, and quality of life through the improvement of trait mindfulness and emotion regulation (9). Hemodialysis is appraised as an uncontrollable, threatening situation, since hemodialysis patients must undergo hemodialysis for their entire lives for survival. Therefore, hemodialysis is not a cure for terminal renal diseases but rather a maintenance therapy (10). It is claimed that repeated mindfulness-based practices cultivate and improve the natural mental capacity of mindfulness, called trait mindfulness (9). Trait mindfulness is described as the mental capacity to pay attention to, be aware of, and accept current experiences in a non-judgmental way (11). This developed mental capacity enables psychological distance through a process of decentered attention, through which one's attention (e.g., thoughts, emotions, and sensations) shifts from the contents of consciousness to the process of consciousness itself. In turn, this can help to stop initial automatic uncontrollable appraisals and broaden attention and awareness to include previously overlooked positive aspects of self, context, or events. Based on this new information, it becomes possible to flexibly select adaptive responses and to reappraise events as beneficial or meaningful (i.e., positive reappraisals). Trait mindfulness also enables individuals to acknowledge and accept their current experiences, even if these experiences are uncomfortable. In addition, trait mindfulness helps individuals to not engage in judgmental or negative thinking or avoidance of these experiences, resulting in less reactivity to stressful situations and increased quality of life (9, 10).

Research supports these theoretical claims, whereby mindfulness meditation has been found to be highly effective for a variety of health outcomes in several psychiatric and medical illnesses (8, 12). For patients undergoing hemodialysis specifically, few studies have demonstrated that mindfulness meditation significantly improves trait

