The inclusion criteria for participation in this study were being a patient with ESRD undergoing hemodialysis three times a week, being aged 18 years old or over, and being able to read and write in Arabic. The exclusion criteria included being a patient with cognitive dysfunction or mental retardation, taking psychopharmacological drugs, or undergoing psychotherapy. A research assistant, who was not involved in the recruitment or patient assessment processes, randomly assigned the participants to the intervention group (n=37) or the control group (n=37) using a simple 1:1 computer-generated sequence. The trial is reported in accordance with the CONSORT guideline.

Determination of the Sample Size

The required sample size was calculated using G-power version (3.1). Given a mixed-design (within groups and between groups) repeated measures ANOVA, power of 0.95, moderate effect size of 0.25, and α of .0125, the required sample size was 56 subjects. A P-value of 0.0125 was set as the significance level for the main analysis tests. The p-value was adjusted due to multiple testing by dividing the p-value of .05 by 4 (number of dependent variables). In a similar study, an attrition rate of 30% and a non-attendance rate of 30% (excluding dropouts) were estimated (18). Thus, taking into consideration of 60% attrition and nonattendance rates, the final total sample size was 89 patients.

Data Collection Instruments

The study data were collected using an Arabic self-report questionnaire with five parts:

Demographic characteristics. This section included a question for each following variable: Age, gender, employment status, nationality, family status, and educational levels.

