Emotion regulation. Emotion regulation is defined as the processes by which individuals influence which emotions they have and how they experience and express these emotions (24). The Arabic version of the Emotion Regulation Questionnaire (ERQ) was used to assess emotion regulation among the study sample (23). The questionnaire items are scored on a 7-point Likert-type scale ranging from 1 (strongly disagree) to 7 (strongly agree) and are divided into two subscales, namely cognitive reappraisal and expressive suppression. Higher scores indicate greater emotion regulation abilities (24). The Arabic version of the ERQ has shown valid and reliable results among the Arab population (23). In our study, the Chronbach's alpha values for the ERQ was 0.81.

kidney disease-quality of life. The Arabic version of the kidney disease-Quality of Life questionnaire (KDQOL-36) is used to assess kidney disease-related quality of life and consists of four subscales: Generic Core (Physical Component Summary (PCS, 12 items) and Mental Component Summary (MCS, 12 items)); Symptoms/Problems (12 items); Burden of Kidney Disease (4 items), and Effects of Kidney Disease (8 items) (25). The scores of the different subscales are calculated according to the KDQOL-36 scoring system. Raw, pre-coded numeric values for each item are transformed linearly to a range of 0 to 100, with higher scores reflecting better kidney disease-quality of life (26). The Arabic version used in this study showed good psychometric qualities among Arab patients with chronic renal failure (25). In our study, the Chronbach's alpha values for KDQOL-36 was 0.93.

Intervention

The experimental group received the Smith's version of mindfulness meditation (27), which is a standardized theory-based intervention found to be effective in improving stress and its related health problems. The Smith's version of mindfulness meditation (27) comprises the following components:

1. Being mindful of breathing, which includes easily taking in a full, deep breath, filling the lungs, simply exhaling, and then breathing naturally. It also includes noticing and simply attending to the air as it flows in and out of the nose and moves deeper into the throat and lungs (5 minutes).

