First, the permission from the instruments used in the study was obtained. Recruitment of participants was conducted by one of the study researchers after obtaining approval to conduct the study from the hospital administrators. The study purposes and protocol were explained to the patients in detail. Patients who agreed to participate in the study and met the eligibility criteria were asked to sign a consent form, and the participating patients were then randomly assigned to the two study groups. The baseline measurements of the study variables were taken using the self-report questionnaires, which were administered by a research assistant who was not involved in any other parts of the study. The study variables were also measured two weeks post the start of the intervention and at the end of the final session for both groups under the same conditions. All measurements were privately taken at the dialysis center.

Data Analysis

SPSS version 25 (SPSS Inc., Chicago, Illinois, USA) was used to analyze the collected data. Prior to the main analysis, outliers and missing data were examined and managed as appropriate. Then, the assumptions of the statistical tests used, normality using histogram graph, homogeneity of variance, and sphericity were checked and managed as appropriate. Mauchly's test of sphericity is used to assess whether the sphericity assumption has been violated. When Mauchly's test of sphericity was significant ($p < .05$),

the degrees of freedom were corrected using Greenhouse-Geisser estimates of sphericity. The comparability of the two groups was evaluated in terms of demographic characteristics and the baseline measurements of the dependent variables using t-test and Chi square, based on the measurements of the dependent variables. The main analysis was conducted with repeated-measures ANOVA (mixed design: within and between groups). A P-value of 0.0125 was set as the significance level for the main analysis tests. The p-value was adjusted due to multiple testing by dividing the p-value of .05 by 4 (number of dependent variables).

Ethical Considerations

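### The emotion-regulation score is undefined and one 'higher is better' rule covers both ERQ subscales; if they are summed without reversal, an effect on reappraisal alone is diluted and a rise in suppression counts as benefit

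*Combined protocol and SAP*

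**What the plan says.** All references are to the protocol.

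- **Data Collection Instruments, Emotion regulation.** The response format for every item is this: "7-point Likert-type scale ranging from 1 (strongly disagree) to 7 (strongly agree"). On the structure of the questionnaire, the protocol describes the items as "divided into two subscales, namely cognitive reappraisal and expressive suppression". The next sentence gives the only scoring direction: "Higher scores indicate greater emotion regulation abilities". Reliability is reported once for the whole instrument: "In our study, the Chronbach's alpha values for the ERQ was 0.81". Reverse scoring is not mentioned, and neither a total, a mean nor a subscale is named as the score analysed.
- **Determination of the Sample Size and Data Analysis.** The significance level comes from "dividing the p-value of .05 by 4 (number of dependent variables"), so emotion regulation is one of four outcomes. "A P-value of 0.0125 was set as the significance level for the main analysis tests". The sample size rests on "power of 0.95, moderate effect size of 0.25, and α of .0125", which gives 56 subjects. The Design section has 74 patients, 37 per group.
- **Introduction.** Mindfulness is expected to lead to positive reappraisal of events and to acceptance of uncomfortable experiences, and it "helps individuals to not engage in judgmental or negative thinking or avoidance of these experiences". Expressive suppression is not mentioned.

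**The concern.** The ERQ as described measures two different strategies, and the plan's theory speaks directly to only one of them. A single scoring rule makes more of either strategy an improvement. This has three consequences.

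1. If the two subscales are added without reversal, suppression contributes variance to the score. Unless suppression rises too, it contributes no signal in the predicted direction. A real effect on reappraisal could then be reported as no effect on emotion regulation.
2. A rise in suppression would be reported as a benefit, both on an unreversed total and on the suppression subscale read by the stated rule. The plan offers no argument for that.
3. Because the score is undefined, the choice between a total and subscales could be made after the data are seen. Testing both subscales as main outcomes would also make the divisor of 4 too small.

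**Working it through.** **Inputs from the protocol.** f = 0.25, alpha = 0.05/4 = 0.0125, target power 0.95, stated N = 56, 74 randomised, k = 2 groups, m = 3 occasions (baseline, two weeks, end of final session).

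**Assumptions, not in the protocol.** Correlation between occasions ρ = 0.5; sphericity; subscales standardised and equally weighted; correlation between subscales r = 0 to 0.4; all 74 analysed; every effect on suppression.

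**Step 1: reproduce the plan's figure.** For the group-by-time interaction, λ = f²·N·m/(1 − ρ), with df1 = (k − 1)(m − 1) = 2 and df2 = (N − k)(m − 1).

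- N = 56: λ = 0.0625 × 56 × 3/0.5 = 21.0, F(2, 108), power 0.952. The stated 56 is reproduced.
- N = 74: λ = 0.0625 × 74 × 3/0.5 = 27.75, F(2, 144), power 0.991.

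**Step 2: effect on an unreversed total.** Let reappraisal move by d_R and suppression by d_S, in SD units. The standardised effect on the sum is (d_R + d_S)/√(2 + 2r). If reappraisal has f = 0.25 and d_S = c·d_R, then f_total = 0.25 × (1 + c)/√(2 + 2r).

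Example with c = 0 and r = 0: the multiplier is 1/√2 = 0.707, so f = 0.177. At N = 74, λ = 13.875 and power is 0.81. With r = 0.4 the multiplier is 1/√2.8 = 0.598, so f = 0.149, λ = 9.91 and power is 0.62.

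| Change in suppression relative to reappraisal | f on the total (r = 0 to 0.4) | Power, N = 56 | Power, N = 74 |
|---|---|---|---|
| Reappraisal tested alone | 0.25 | 0.95 | 0.99 |
| Unchanged (c = 0) | 0.177 to 0.149 | 0.65 to 0.46 | 0.81 to 0.62 |
| Falls half as much (c = −0.5) | 0.088 to 0.075 | 0.13 to 0.09 | 0.18 to 0.12 |
| Equal and opposite (c = −1) | 0 | 0.0125 | 0.0125 |
| Rises half as much (c = +0.5) | 0.265 to 0.224 | 0.97 to 0.89 | 0.996 to 0.97 |

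**Step 3: sensitivity to the weights.** The protocol does not give item counts per subscale. With an assumed 6:4 weighting towards reappraisal, power at N = 74 over the same range of r is 0.93 to 0.81 with suppression unchanged, 0.54 to 0.38 if it falls half as much, and 0.10 to 0.07 if it falls equally. The loss is smaller but in the same direction.

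**Step 4: cost of the alternatives.** Reappraisal as the single emotion-regulation outcome keeps alpha at 0.0125 and N at 56. Two ERQ subscales as main outcomes make five tests: alpha = 0.05/5 = 0.01, N = 58 for power 0.95, and power 0.989 with 74.

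**The case against.** The strongest reply is that the protocol never says a total is analysed. The indirect signs do not settle it. The KDQOL-36 also has one reliability figure and counts once among the four outcomes, although its subscales are scored separately. The sentence on direction would also fit a total with suppression reversed. In that case a fall in suppression would add to the effect and this dilution would not arise. This stands: the unreversed total is the most natural reading of one direction, one alpha and no mention of reversal, but it remains an inference.

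A reader might also infer that the plan predicts a fall in suppression, or that the predicted effect will be cancelled. The documents support neither. The Introduction speaks of acceptance and avoidance of experiences and never names expressive suppression, and the protocol's definition of emotion regulation includes how emotions are expressed. Cancellation needs changes of about equal size in opposite directions, and the protocol gives no figures for that. If suppression rises alongside reappraisal, the total loses little or no power.

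The reply does not remove the point. If the subscales are analysed separately, the stated rule still treats more suppression as better, and two ERQ tests do not fit within a divisor of 4. If suppression is reversed, the plan has to say so. Dilution on an unreversed total needs no fall in suppression: no change is enough over the range of r used here.

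**Conclusion.** The concern holds in conditional form. The plan leaves the ERQ score undefined and applies one direction to two strategies, while its theory names a rise in one of them only. If an unreversed total is analysed, an effect confined to reappraisal is diluted: power with 74 patients drops from 0.99 to 0.81–0.62. It is largely lost (0.18–0.12) if suppression falls half as much. A rise in suppression would be counted as improvement; if it is half as large as the rise in reappraisal, power is 0.996–0.97.

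These sizes rest on the plan's f = 0.25 being the effect on reappraisal and on the assumptions listed in the check. They also take all 74 as analysed, so dropout would lower every figure. They show how much the score definition can matter; they do not forecast what the trial will find.

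**What to change.** - Do not analyse an unreversed ERQ total.
- Prespecify cognitive reappraisal, the strategy the theory names, as the emotion-regulation outcome in the four-test family at alpha 0.0125, with higher scores as improvement.
- Analyse expressive suppression separately as a secondary outcome with its own stated direction.
- Replace the general sentence on higher scores with one direction per subscale, and report reliability for each subscale.
- If both subscales are kept as main outcomes instead, count them separately and use a divisor of 5 (alpha 0.01).

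The cost is a change of wording and one extra secondary analysis on data the questionnaire already collects. Alpha and sample size stay as they are under the first option; under the second, N rises from 56 to 58, still below the 74 randomised (before dropout). The downside is that the conclusion on emotion regulation will then refer to reappraisal and not to the ERQ as a whole.

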2. Being mindful of the body, which includes attending to how the body feels from head to toes and noticing any sensations that come and go. Upon noticing a sensation, the individual must gently note it, let it go, and continue attending to how the body feels (5 minutes).
3. Being mindful of thought, which includes attending to the mind as thoughts come and go. Whenever a thought or feeling comes to mind, the individual should just notice it, let it go, and continue attending to the mind repeatedly (5 minutes).
4. Being mindful of sounds, which includes attending to the sounds one hears, without thinking about them. The individual must gently notice the sound, let it go, and continue waiting (5 minutes).
5. Being mindful of taste, which includes imagining a wonderful bowl of pieces of one's favorite fruit and simply attending to a taste sensation, without thought, analysis, or effort (5 minutes)
6. Full meditation, which includes gently opening one's eyes and being mindful of the world of the moment, quietly attending, and waiting. When noticing something, be it a sight, sound, thought, or sensation, the individual must let it go and then resume attending, doing nothing else, and waiting for what comes next (5 minutes).

The experimental group received 30-minute individually administered, guided, chairside interventions during their hemodialysis sessions. This protocol has been found to

be feasible and effective for patients undergoing hemodialysis (6). Smith (2005) explained in his ABC relaxation theory that at least two and preferably five weekly 30-minute sessions of actual training of mind-body therapies should be provided to evoke relaxation, relieve stress, and improve health in general populations. However, for hemodialysis patients, it has been suggested that brief program formatting with at least 400 total minutes may lead to greater health benefits (18). Accordingly, the experimental group received 30-minute mindfulness meditation sessions 3 times a week for 5 weeks (450 minutes)

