The participants also received a 2-hour foundation course which was introduced and supervised by one of the study researchers prior to the actual training sessions and which taught the participants the intervention basics, benefits, protocol, and method of access. To ensure the consistent delivery of the intervention, the researcher recorded the intervention instructions in Arabic based on the Smith (2005) protocol and sent the audio-recorded instructions to the participants via WhatsApp or email. The audio-recorded intervention contents were validated by 2 psychologists and experts in meditation. The recorded intervention instructions were accessed by the participants during the sessions using their cell phones and headsets, as recommended (18). This method allowed for up to 3-5 participants to listen to the instructions and perform the intervention simultaneously.

The researcher who was responsible for developing the study intervention and supervising the intervention delivery was an experienced mind-body practitioner who had received a 4-day training course on mindfulness meditation. The researcher attended the sessions to manage any potential interruptions and evaluate the intervention delivery. The participants' privacy was maintained using curtains surrounding each participant during the intervention. The participants were asked not to share any information related to the intervention with the participants in the control group.

The participants in the control group were instructed to sit with their eyes closed and relaxed for 30 minutes 3 times a week for 5 weeks during hemodialysis sessions to control for the nonspecific effects of social interaction and environment (35). The timings of the control group sessions were similar to those of the experimental group, whereby if a given experimental group intervention lasted for 30 minutes, the control group participants would be asked to sit with their eyes closed and relax for 30 minutes also.

Procedure

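### The control condition matches session time and setting but not researcher contact, so the protocol should not say that it controls for social interaction

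*Combined protocol and SAP*

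**What the plan says.** All of the relevant text is in the Intervention section unless another section is named.

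- **Control arm.** "The participants in the control group were instructed to sit with their eyes closed and relaxed for 30 minutes 3 times a week for 5" (the last figure counts weeks; the rest takes place at dialysis). The stated purpose is "to control for the nonspecific effects of social interaction and environment". On scheduling, "The timings of the control group sessions were similar to those of the experimental group".
- **Meditation arm, sessions.** Guided chairside sessions on the same pattern, which the protocol totals at 450 minutes. Recorded instructions are played through the patient's own phone and headset.
- **Meditation arm, course.** "The participants also received a 2-hour foundation course which was introduced and supervised by one of the study researchers prior to the actual training sessions". It "taught the participants the intervention basics, benefits, protocol, and method of access".
- **Researcher presence.** "The researcher attended the sessions to manage any potential interruptions and evaluate the intervention delivery". The text does not say whether this covers control sessions.
- **Outcomes and assessment.** Trait mindfulness, perceived stress, emotion regulation and quality of life are all measured by self-report questionnaire (Data Collection Instruments). A research assistant with no other part in the study administers the baseline questionnaires, and later measurements are taken under the same conditions in both groups (Procedure).
- **Use of the result.** The Introduction expects insight into how mindfulness meditation affects quality of life, and hopes to inform adoption in Kuwaiti hospitals.

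**The concern.** The protocol credits the control condition with removing two nonspecific influences, the environment and social interaction. If one of them still differs between the arms, a reader will take a significant result as evidence for meditation practice with researcher attention already excluded, and it has not been. Teaching benefits to one arm only adds a second difference, in expectation. Self-report outcomes are open to both.

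The planned two-group repeated-measures ANOVA cannot separate these influences, because practice, contact and expectation all change together with allocation. What is at stake is the permissible conclusion, in particular any statement about mechanism. The randomised comparison itself remains valid as a comparison of what the two arms actually received.

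**Working it through.** **Step 1. Reproduce the protocol's own figure.** Session dose is 30 minutes x 3 per week x 5 weeks = 450 minutes, which agrees with the stated total. The control schedule gives the same: 30 x 3 x 5 = 450 minutes. Session time is matched.

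**Step 2. Add what lies outside the sessions.** The course is 2 hours = 120 minutes. Scheduled activity is 450 + 120 = 570 minutes in the meditation arm and 450 in the control arm. The difference is 120 minutes, and 120/450 = 27%. These are scheduled minutes. They are not measured contact, since the 450 minutes are headset audio in one arm and silent rest in the other. The figure that bears on social interaction is the course: 120 versus 0 minutes.

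**Step 3. Confirm which arm takes the course.** The sentence says only that the participants received it. Three features place it in the meditation arm: it follows directly on the experimental group's session dose, it teaches the intervention itself, and participants are later asked not to pass information about the intervention to controls. A course teaching controls the intervention would defeat that request.

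**Step 4. Set the stated purpose against the design.**

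| Element | Meditation arm | Control arm | Matched? |
|---|---|---|---|
| Session length and schedule | 450 min | 450 min | Yes |
| Setting | Dialysis unit | Dialysis unit | Yes |
| Researcher-supervised course | 120 min | None described | No |
| Teaching of benefits | Yes | None described | No |
| Researcher at sessions | Yes | Not stated | Unknown |
| Questionnaire conditions | Same | Same | Yes |

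The guided audio is left out of the table because it is the means by which the meditation is delivered. It is a weak example of a nonspecific imbalance.

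**Step 5. Ask what an unmatched influence could do.** The documents give no figure for the effect of attention or expectancy, so this step is an illustration on assumptions. Suppose the imbalance shifts self-report by d standard deviations and meditation practice has no effect. Take a two-sample t-test at one time point with 37 per arm (Design) and two-sided alpha 0.0125 (Data Analysis). The noncentrality is d x sqrt(37/2), with 72 degrees of freedom. The chance of a significant result per outcome is:

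- d = 0: 1.25%
- d = 0.1: 2.1%
- d = 0.2: 4.9%
- d = 0.4: 20.8%

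For comparison, the same test has 80% power at a difference of 0.79 SD. A shift in the assumed range would usually not reach significance alone, but it would add in full to any real effect of practice.

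**The case against.** The strongest reply is that the quoted sentence names only social interaction and environment, and that the environment half is met. This stands. Expectation of benefit is not something the protocol claims to control, so that part is an unacknowledged limitation. The contradiction rests on social interaction alone.

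Two safeguards also deserve credit: independent administration of the questionnaires under like conditions, and the request not to share intervention content with controls. They reduce assessor influence and contamination. They do not equalise contact or expectation.

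It can also be said that the aim already refers to a mindfulness-based intervention, which can be read as the whole package. That is fair, and it makes the correction easier, but it does not repair the purpose stated for the control condition. The citation given for that purpose is numbered 35 and the reference list as supplied ends at 29, so its basis cannot be checked here.

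Three stronger readings are tempting, and the documents support none of them:

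- **That attention and expectancy explain a difference as well as mindfulness does.** Nothing in the documents sizes either one. Even the top of the assumed range above, 0.4 SD, is about half of the 0.79 SD detectable difference.
- **That the meditation arm has 27% more contact.** That is a ratio of scheduled minutes. With attendance at control sessions unstated, the true ratio of contact is unknown.
- **That no effect can be attributed to mindfulness.** The design estimates the effect of a package that contains mindfulness. What it cannot do is apportion that effect among the components.

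**Conclusion.** The point holds as a correction to a stated property of the design. The protocol says that the control condition handles nonspecific social effects, yet it describes a 120-minute researcher-supervised course for one arm and none for the other. Nothing elsewhere in the document restores the balance. The environment is largely controlled.

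The result can support a conclusion about the meditation package against unguided rest. It cannot show that practice, apart from attention and expectation, produced the difference, nor isolate a mechanism. The conclusion assumes that the course went to the meditation arm only, which the context strongly supports, and that contact not described for controls was not given. The direction of any bias would probably favour meditation; its size is unknown, and the 0.1 to 0.4 SD range is an assumption used only for scale.

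**What to change.** 1. In the Intervention section, replace the stated purpose of the control condition with: *matches session time, schedule and setting; researcher contact in the foundation course and expectation of benefit are not matched.*
2. State whether the researcher attended control sessions.
3. Define the contrast as the meditation package (course, guided audio, supervision) versus unguided rest, and use that wording in the conclusions.
4. Do not claim that nonspecific social effects were controlled, or that a difference between arms isolates the mindfulness mechanism.

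These are changes of wording. They need no extra sessions, staff or patients and can be made even if delivery is complete. The cost is a narrower claim, although a package effect still informs a decision on adopting the package.

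Taking the benefits content out of the course, or changing the recruitment explanation, is not needed for this point. Either would alter the intervention or consent-related material, and the 2-hour contact difference would remain.
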